3.15.1 Pyrexia

Pyrexia has been observed in adult subjects receiving dabrafenib. In a minority of cases pyrexia was accompanied by symptoms such as severe chills/rigors, dehydration, and hypotension, which in some cases can lead to acute renal insufficiency. Serious non-infectious febrile events have been observed and typically occurred within the first month of therapy.

Subjects should be instructed on the importance of immediately reporting febrile episodes. Therapy with dabrafenib should be interrupted if the patient's temperature is $\geq 38.5^{\circ}\text{C}$ or 101.3° Fahrenheit. In the event of a fever, the subject should be instructed to take anti-pyretics (e.g. ibuprofen or acetaminophen/paracetamol as appropriate to control fever). The use of oral corticosteroids should be considered in those instances in which anti-pyretics are insufficient. Monitor serum creatinine and other evidence of renal function during and following severe events of pyrexia.

Guidelines regarding management and dose reduction for pyrexia considered to be related to dabrafenib are provided in [Table 3-12](#).

Table 3-12 Mandatory dose modification and recommended clinical management for pyrexia^{a, b}

Occurrence	Recommended adverse event management guidelines	Mandatory dose modification requirements
Any	
 Clinical evaluation for infection and hypersensitivity^c Laboratory work-up^c Hydration as required^d 	
 See relevant row below
1st Event^b :	
 Administer anti-pyretic treatment^e as clinically indicated^f 	
 Interrupt dabrafenib Trametinib may continue (Interrupt trametinib for fever higher than 40°C (104°F)) Once pyrexia resolves to baseline ($<38.5^{\circ}\text{C}$ (101.3°F)), restart dabrafenib at the same dose level (for pyrexia of 38.5°C (101.3°F) to 40°C (104°F)) or at the lower dose level (Appendix 2, dose reduction column) (for pyrexia $> 40^{\circ}\text{C}$ (104°F)) and restart trametinib (if applicable) If fever was associated with dehydration, hypotension, rigors or chills, or renal failure, interrupt dabrafenib and trametinib^g
2nd Event^f	
 Same as for 1st event, and 
 Consider oral corticosteroids (i.e. prednisone 10mg) for at least 5 days or as clinically indicated^g 	
 Same as first event
Subsequent Events:	
Within 3 days of onset of pyrexia:
 
 Optimize oral corticosteroid dose as clinically indicated for recalcitrant pyrexia^f If corticosteroids have been tapered and pyrexia recurs, restart steroids 	
 Interrupt dabrafenib Trametinib may continue (Interrupt trametinib for fever higher than 40°C (104°F)) Once pyrexia resolves to baseline, restart dabrafenib at lower dose (appendix 2, dose reduction column) and restart trametinib (if applicable). Re-escalation of dabrafenib is allowed if no episode of pyrexia is observed in the 4 weeks subsequent to dose reduction.

BUN = blood urea nitrogen; CRP = C-reactive protein
 
a. Pyrexia is defined as a body temperature equal to or above 38.5° Celsius or 101.3° Fahrenheit.
 
b. For subjects experiencing pyrexia complicated by rigors, severe chills, etc., a clinical evaluation and laboratory work-up is mandatory for each event; anti-pyretic treatment should be started immediately at the first occurrence and prophylactic anti-pyretic treatment is recommended.
 
c. Thorough clinical examination for signs and symptoms of infection or hypersensitivity is required; laboratory work up should include full blood count, electrolytes, creatinine, BUN, CRP, and liver function tests, blood culture and urine culture.
		

- d. Oral hydration should be encouraged in subjects without evidence of dehydration. Intravenous hydration is recommended in subjects experiencing pyrexia complicated by dehydration/hypotension.
- e. Anti-pyretic treatment may include acetaminophen (paracetamol), ibuprofen, or suitable anti-pyretic medication according to institutional standards. Prophylactic anti-pyretic treatment may be discontinued after three days in the absence of pyrexia
- f. In subjects experiencing pyrexia complicated by rigors, severe chills, etc., which cannot be controlled with anti-pyretic medication, oral corticosteroids should be started at the 2nd event and doses should be gradually increased for subsequent events.
- g. Dabrafenib should be reduced by one dose level (Appendix 2, dose reduction column) at discretion of the investigator if pyrexia is accompanied by severe rigors which cannot be managed by best supportive care, including increasing doses of oral steroids.

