3.15 Guidelines for Dose Modifications and Toxicity Management for Combination Therapy

If treatment related toxicities occur when dabrafenib is used in combination with trametinib then both treatments should be simultaneously dose reduced, interrupted or discontinued with the exception shown below:

- Dose modification is necessary for only dabrafenib
 - Mild to moderate pyrexia ([Section 3.15.1](#))
 - Uveitis ([Section 3.13.5](#) and [Section 3.14](#))
- Dose modifications are necessary for only trametinib:
 - Retinal vein occlusions (RVO) and retinal pigment epithelial detachment (RPED) ([Section 3.13.5](#))
 - Left ventricular ejection fraction (LVEF) reduction (asymptomatic, [Section 3.12.3.1](#))
 - Pneumonitis and interstitial lung disease (ILD) (grade 4, [Section 3.13.7](#))

The severity of adverse events (AEs) will be graded utilizing the NCI-CTCAE v4.03 ([NCI 2009](#)). Guidelines for dose modifications and interruptions for management of common toxicities associated with dabrafenib are provided in this section.

Trametinib dose reduction for patients enrolled in all parts of the study should follow dose reduction column in the trametinib dosing nomogram in Appendix 2.

Dabrafenib dose reduction should follow the dose reduction column in the dabrafenib dosing nomogram in Appendix 2 provided for patients enrolled in Part C and Part D, as described below

- Dabrafenib dose modification levels in Part C
 - If a subject is dosed at Dose Level 1, and requires dose reduction, treatment must be discontinued
 - If a subject is dosed at Dose Level 2, and requires dose reduction, follow the dose reduction column in dosing nomogram
- Dabrafenib dose modification levels in Part D.
 - Follow dose reduction column in dosing nomogram

Nomograms for each dosing level are provided in [Appendix 2](#).

If a second dose reduction is required, the treatment should be discontinued.

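### From the third fever on, Table 3-12 drops the mandatory rule to interrupt trametinib as well as dabrafenib in complicated fever of 38.5 to 40 °C

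*Protocol*

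**What the plan says.** Table 3-12 has one column of recommended management and one of mandatory dose modification. In the mandatory column:

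- **First event.** Dabrafenib is interrupted. Trametinib may go on unless fever exceeds 40 °C. A further bullet covers complicated fever: "If fever was associated with dehydration, hypotension, rigors or chills, or renal failure, interrupt dabrafenib and trametinib".
- **Second event.** "Same as first event".
- **Subsequent events.** The row does not refer back. Dabrafenib is interrupted. For trametinib: "Trametinib may continue (Interrupt trametinib for fever higher than 40" °C). Then: "Once pyrexia resolves to baseline, restart dabrafenib at lower dose (appendix 2, dose reduction column) and restart trametinib (if applicable"). Finally: "Re-escalation of dabrafenib is allowed if no episode of pyrexia is observed in the 4 weeks subsequent to dose reduction". The complicated-fever bullet is absent.

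Two footnotes show that complicated fever is foreseen beyond the first event. Footnote b says that for such fever "a clinical evaluation and laboratory work-up is mandatory for each event". Footnote f says that where anti-pyretics fail, "oral corticosteroids should be started at the 2nd event and doses should be gradually increased for subsequent events".

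Section 3.15, which governs combination therapy, makes joint modification of both drugs the default for treatment-related toxicity. Among the exceptions where only dabrafenib changes it lists "Mild to moderate pyrexia", and it does not define that term.

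**The concern.** A mandatory safety rule is looser at recurrence than at first occurrence, and the protocol does not say why. A child with a third fever of 39 °C and chills may stay on trametinib. At the first and second fever the same episode obliged the site to interrupt both drugs.

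The row is not a remote case. Section 1.7.2 reports that about one-third of adults who developed pyrexia on the full combination dose had three or more events. It adds that pyrexia can come with rigors, dehydration and hypotension, in some cases leading to acute renal insufficiency. Section 1.4 expects that children on the combination may have more frequent and more severe pyrexia than on dabrafenib alone.

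At stake are the safety of individual children and the consistency of trametinib handling between sites.

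**Working it through.** The plan gives no figure to reproduce. The check is a comparison of the rules, followed by simple counts.

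**1. The rows side by side, for pyrexia (38.5 °C or above by footnote a)**

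| Event | Complicated fever, 38.5–40 °C | Fever above 40 °C |
|---|---|---|
| First | Interrupt both drugs | Interrupt both drugs |
| Second | Interrupt both drugs | Interrupt both drugs |
| Third or later | Interrupt dabrafenib; trametinib may continue | Interrupt both drugs |

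The first-event clause has no upper temperature limit, and above 40 °C every row interrupts trametinib anyway. The difference therefore lies exactly between 38.5 and 40 °C.

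**2. Does anything else in the table restore the clause?** The row for any event only points to the rows below it. Footnote a defines pyrexia. Footnotes b to e cover work-up, hydration and anti-pyretics, and footnote f covers steroids. Footnote g allows a discretionary reduction of dabrafenib alone. None deals with holding trametinib.

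**3. Do rules elsewhere cover it?**

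- Table 3-6 interrupts study drug for related events of intolerable Grade 2, Grade 3 or Grade 4. Section 3.14 limits these general rules to events without a specific guideline. Pyrexia has one, but a complication graded as its own event may still fall under Table 3-6.
- Table 3-13 acts on a creatinine rise of at least 50% (and at least 0.20 mg/dL). At a first occurrence it interrupts both drugs below a 100% rise and stops both from 100%. At a second occurrence it stops dabrafenib and continues trametinib. It does not address rigors, chills, hypotension or dehydration.
- Section 3.14 asks investigators to lean towards caution. That is general advice beside a specific mandatory row.

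What is left is chiefly lower-grade complications.

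**4. How many children?** Enrolment figures are from the Amendment 9 rationale, as of 17 July 2020.

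- Parts C and D: 18 + 30 = 48.
- All parts: 50 + 41 + 18 + 30 = 139.
- Still on treatment, at most: 139 − 80 discontinued = 59.
- If the 13 rollover patients are not among the 80: 59 − 13 = 46.

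The 46 to 59 include Parts A and B, which give trametinib alone and are outside Table 3-12. The Part C and D share is not stated.

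**The case against.** The strongest case is that the difference may be deliberate. Section 1.7.2 says, without qualification, that trametinib can go on during fever in combination patients. The text of Section 3.15.1 treats pyrexia as a dabrafenib effect. At the third event the table shifts action onto dabrafenib, with a mandatory restart at a lower dose and re-escalation only after four fever-free weeks, and it asks for steroids to be optimised. Table 3-13 has a similar pattern, continuing trametinib at a second renal occurrence. This stands as far as intent goes: the text does not prove a drafting slip. It does not explain the difference, because the Section 1.7.2 statement does not separate complicated from simple fever and would apply equally to the first two events.

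A reader might infer that the row contradicts Section 3.15. That holds on one reading only. If complicated fever is more than mild to moderate, the Section 3.15 default is to interrupt both drugs, and the row departs from it. Even then a site that holds both breaks nothing in the row, which says only that trametinib may continue. If 39 °C with chills counts as mild to moderate, row and section agree, and only the contrast with the first two events remains. Since the term is undefined, a conflict cannot be stated as fact.

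A reader might also infer that trametinib must continue, or that pyrexia management as a whole loosens. Neither is supported: continuation is optional, and the dabrafenib rule tightens.

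The reach is also small. Enrolment is closed, and Section 3.15.1 says that serious non-infectious febrile events typically came in the first month and that complications accompanied a minority of cases in adults. This reduces the number affected but does not bring it to zero, because recurrent fever in adults was common.

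**Conclusion.** The point holds as a minor safety correction. Under the mandatory column as written, a third or later complicated fever of 38.5 to 40 °C no longer requires interrupting trametinib, although the first and second did, and no reason is given.

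The practical gap is chiefly lower-grade complications in Part C and D children still on combination treatment. Their number is unknown; they come from the 48 enrolled in those parts. The conclusion assumes that sites follow the specific row over the general text, and that the adult pattern of recurrent fever is some guide to children. Whether Section 3.15 is also breached depends on how its undefined term is read, and the verdict does not rest on it. The dose-limiting toxicity definition, endpoints, sample size and analyses are unaffected.

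**What to change.** Add the existing first-event clause to the mandatory column of the subsequent-events row in Table 3-12: "If fever was associated with dehydration, hypotension, rigors or chills, or renal failure, interrupt dabrafenib and trametinib". If the difference was intended, state the reason in that row instead.

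The cost is one repeated clause, made by amendment or letter to sites. It needs no new procedure and no new data.

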3.15.2 Renal insufficiency

Cases of renal insufficiency have occurred in adult subjects receiving dabrafenib. Prior to start of study treatment, concomitant medications should be reviewed for the potential risk of inducing nephrotoxicity and concomitant medications should be modified if clinically possible.

Guidelines regarding management and dose reduction for renal insufficiency considered to be related to study treatment by the investigator are provided in [Table 3-13](#).

For the purposes of this guideline, increases from baseline should have *at least* the following *absolute* increase to qualify for the noted *percent* increase in this guideline. The normal serum creatinine values anticipated for young patients on this protocol are near the reporting limits of the laboratory analysis, and are thus subject to variability in reported results and high calculated percent changes. The absolute increase values are intended to alleviate dosing changes due to spuriously high calculations for percentage change.

For a 25% increase – that must also be at least a 0.10mg/dL absolute increase

For a 50% increase – that must also be at least a 0.20 mg/dL absolute increase

For a 100% increase – that must also be at least a 0.40 mg/dL absolute increase

Table 3-13 Mandatory dose modifications and required clinical management guidelines for renal function alterations

For subjects with creatinine rise $\geq 50\%$ from baseline :	Required adverse event management guidelines	Mandatory dose modification requirements
1 st occurrence	
 ● If patient has fever: treat pyrexia as per Table 3-12 (please note NSAIDs can induce renal insufficiency, especially in patients with dehydration); consider IV hydration ● Pediatric nephrology consult is recommended ● Re-check within 24 hours 
 ● If creatinine rise is < 25% from baseline: 
 ● Monitor creatinine weekly for 4 weeks to ensure levels remain within 25% of baseline ● If creatinine rise is $\geq 25\%$ but < 50% from baseline: ● Monitor creatinine at least twice 	
 ● If creatinine rise is < 25% from baseline: 
 ● Continue dabrafenib and trametinib at current dose ● If creatinine rise is $\geq 25\%$ but < 50% from baseline: 
 ● Continue dabrafenib and trametinib at current dose

For subjects with creatinine rise \geq 50% from baseline :	Required adverse event management guidelines	Mandatory dose modification requirements
	weekly, can decrease frequency if creatinine rise < 25% from baseline 
 ● Avoid nephrotoxic agents ● If creatinine rise is \geq 50% but < 100% from baseline: 
 ● Monitor creatinine at least twice weekly ● Avoid nephrotoxic agents 	
 ● If creatinine rise is \geq 50% but < 100% from baseline: 
 ● Interrupt dabrafenib and trametinib ● May restart dabrafenib at reduced dose and trametinib at reduced dose if creatinine rise returns to < 25% from baseline (see Appendix 2 dosing nomogram “Dose Reduction” columns for trametinib and dabrafenib) ● If creatinine rise is \geq 100% from baseline: 
 ● Permanently discontinue dabrafenib and trametinib
2 nd occurrence	See guidance for first occurrence	
 ● Permanently discontinue dabrafenib and continue trametinib

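### Table 3-13 continues trametinib at a second creatinine rise of 100% or more, although a rise of that size permanently ends both drugs at a first occurrence

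*Protocol*

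**What the plan says.** Section 3.15.2 covers renal insufficiency that the investigator considers related to study treatment. The title of Table 3-13 makes its dose modifications mandatory. The table is entered at a creatinine rise of 50% or more from baseline, with a re-check within 24 hours. A 100% rise counts only with an absolute condition: "that must also be at least a 0.40 mg/dL absolute increase".

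For a **first occurrence** the dose column has four tiers:
- Below 25%, and 25% to <50%: both drugs continue at the current dose.
- 50% to <100%: both are interrupted, and both may restart at reduced dose once the rise is below 25%.
- 100% or more: "Permanently discontinue dabrafenib and trametinib".

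For a **second occurrence** the dose column has a single untiered line: "Permanently discontinue dabrafenib and continue trametinib". The back-reference "See guidance for first occurrence" stands only in the management column.

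Section 3.15 sets the default for combination therapy: "both treatments should be simultaneously dose reduced, interrupted or discontinued with the exception shown below". Under the exception heading "Dose modification is necessary for only dabrafenib" it lists mild to moderate pyrexia and uveitis, and no renal event.

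**The concern.** Within one mandatory column, the same size of rise ends trametinib when it comes first and leaves trametinib running when it comes as a recurrence. One would expect a recurrence to be handled at least as strictly, as in the QTc table (Section 3.12.2), where a recurrence permanently stops study treatment. Section 3.15.2 gives no reason for relaxing the trametinib rule in the top tier.

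At stake is a safety instruction. A site that follows the cell literally keeps a child on trametinib through a rise that the same table treats as the end of both drugs at a first event.

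**Working it through.** The protocol states no figure to reproduce. The check compares the cells, tests whether the case can arise, and sizes it.

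**1. Dose action by size of rise (Table 3-13)**

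| Rise | First occurrence | Second occurrence |
|---|---|---|
| 50% to <100% | Interrupt both; reduced-dose restart possible below 25% | Dabrafenib stopped for good, trametinib continues |
| 100% or more | Both stopped for good | Dabrafenib stopped for good, trametinib continues |

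In the top tier the trametinib action goes from permanent stop to uninterrupted continuation.

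**2. Can a child reach it?** A first event of 100% or more on re-check ends both drugs, so the case needs a first event below 100%. There are two routes:
- Re-check below 50%: both drugs continue.
- Re-check 50% to <100%: both are interrupted and may restart at reduced dose. Section 3.15 closes this route to Part C children on dabrafenib Dose Level 1, who discontinue if they need a reduction.

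**3. Where the 100% tier starts.** Threshold = max(2 × baseline, baseline + 0.40), in mg/dL:
- baseline 0.2: max(0.4, 0.6) = 0.6
- baseline 0.3: max(0.6, 0.7) = 0.7
- baseline 0.4: max(0.8, 0.8) = 0.8
- baseline 0.5: max(1.0, 0.9) = 1.0

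**4. Worked case, assumed baseline 0.40 mg/dL**
- First event 0.70: 0.30/0.40 = +75%, absolute +0.30 (floor for the 50% tier is 0.20). Both drugs are interrupted.
- Restart needs a rise below 25%: below 0.40 × 1.25 = 0.50.
- Second event 0.85: 0.45/0.40 = +112.5%, absolute +0.45 (floor 0.40). Dabrafenib stops and trametinib continues.
- The same 0.85 on re-check of a first event would have stopped both.

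**5. How severe is 0.85 mg/dL?** Against the age-specific upper limits in Section 5.2.1.1:
- 1 to <2 years: 0.85/0.6 = 1.42 × ULN
- 2 to <6 years: 0.85/0.8 = 1.06 × ULN
- 6 to <10 years: 0.85/1.0 = 0.85 × ULN

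**6. Who is exposed?** The Amendment 9 rationale gives 18 children in Part C and 30 in Part D, so 48 at most, with all cohorts closed. Across all four parts, at most 139 − 80 = 59 had not discontinued treatment at 17-Jul-2020. The Part C and D share, and the rate of second renal events, are not given.

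**7. Does other text settle the tier?**
- The back-reference sits in the management column, while the dose column carries its own explicit instruction. It brings in the 24-hour re-check, but the first-occurrence management bullets stop at <100%, so it supplies no monitoring frequency for this tier.
- For febrile children the management column says "If patient has fever: treat pyrexia as per Table 3-12", and Table 3-12 says "If fever was associated with dehydration, hypotension, rigors or chills, or renal failure, interrupt dabrafenib and trametinib". That covers only fever with renal failure, a term it does not define, and it interrupts trametinib where the top tier of Table 3-13 stops it for good.

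**The case against.** The best defence is attribution. Section 3.15.2 opens with renal insufficiency in adults on dabrafenib, Section 1.4 lists it as an event of special interest for dabrafenib, and Section 1.3.3 describes renal toxicity in juvenile rats given dabrafenib. Section 1.7.1 reports no significant effect of mild or moderate renal impairment on trametinib PK, while noting no data in severe impairment. Holding both drugs at a first event and removing the suspected one when it recurs is coherent. This stands for a second rise of 50% to <100%. It does not explain the top tier, where the table stops trametinib at a first event despite the same attribution.

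A reader might infer a literal contradiction. The documents do not support that: the two rows govern different events, and no single event receives two instructions. It is an inconsistency between rows.

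A reader might also infer from Section 3.15 that any renal exception for dabrafenib alone is an error. The exception list is not exhaustive: for pneumonitis it names only grade 4, yet Table 3-11 lets dabrafenib continue at grades 2 and 3 too. Absence from the list is therefore weak evidence, and if it counted it would equally condemn the 50% to <100% action, which attribution can explain.

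Finally, stopping both drugs removes all study therapy from children with relapsed or refractory disease. That cost is real, but the table already accepts it for a first event of the same size.

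**Conclusion.** The point holds for one tier: a treatment-related second rise of 100% or more and at least 0.40 mg/dL. There the mandatory cell reverses the table's own first-occurrence rule for trametinib without a stated reason, and the case is reachable.

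The size is minor. It concerns Parts C and D only, needs two renal events with the second at least double baseline, and has no event rate that can be put on it. Section 6.3 allows discontinuation at the investigator's discretion, and Section 3.14 urges caution where treatment-related toxicity is possible. These soften the consequence but leave the cell as written. No RP2D, endpoint or analysis is affected.

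Two stronger readings should be avoided. The tier does not by itself show severe renal injury, since 0.85 mg/dL lies below the protocol ULN at 6 to <10 years. Nor do the documents show that continuing trametinib at a second rise of 50% to <100% is wrong.

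The conclusion assumes that a first event re-checked below 100% counts as an occurrence and that the first-occurrence tiers apply to the re-checked value, which is the natural reading of the table.

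**What to change.** Split the second-occurrence dose cell of Table 3-13 into two tiers:
- Rise of at least 50% but below 100%: dabrafenib is permanently discontinued; trametinib may continue.
- Rise of 100% or more: as for first occurrence, "Permanently discontinue dabrafenib and trametinib".

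This changes one table cell and adds no visits or procedures. The downside is that a few children may lose trametinib. Adding the second rise of 50% to <100% to the dabrafenib-only list in Section 3.15 would be optional tidying.
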